### **③ Statistical Analysis Methods**

**A. Enrollment and Completion Status** The enrollment and completion status for each center will be listed, including whether enrolled cases met the inclusion and exclusion criteria. The actual number of enrolled cases, excluded cases, and dropped-out cases for each center will be counted individually, and the FAS, PPS, and SS will be defined.

**B. Baseline Balance Analysis** Baseline is defined as before radiotherapy (-7 to 0 days). A comparability analysis of the basic demographic characteristics, general conditions, and baseline status (pre-treatment) at the time of enrollment will be conducted for the experimental and control groups. Specifically, quantitative data conforming to a normal distribution will use the independent samples t-test, quantitative data conforming to a skewed distribution will use non-parametric tests, ordinal data will use the Kruskal-Wallis test, and categorical data will use the  $\chi^2$  test or Fisher's exact test.

#### **C. Comparison of Factors Affecting Trial Evaluation**

[figure not shown]
**a. Analysis of Concomitant Medication Use** The frequency and percentage of concomitant medication use will be listed for the cases. Group comparison will be performed using the  $\chi^2$  test or Fisher's exact test.

**b. Analysis of Medication Compliance** The frequency and percentage of cases with medication compliance < 80%, and > 120% , 80% ~ 120% will be listed. Group comparison will be performed using the  $\chi^2$  test or Fisher's exact test.

**c. Time Exposed to Treatment** Treatment duration (days) = Time of last dose – Time of first dose + 1.

The number of cases, mean, standard deviation, median, minimum, and maximum will be calculated. Group comparison will be performed using the independent samples t-test or the Wilcoxon rank-sum test.

## **8. Study Steps and Technical Route**

## 9. Data Confidentiality Plan

All records related to the subject's identity shall be kept confidential, and these materials will not be made public beyond the scope permitted by relevant laws and/or regulations. The subject's name will not be provided to the sponsor. Only the subject's number and initials of the name will be recorded on the case report form. If the subject's name appears in any other document (e.g., pathology reports), it must be redacted before providing copies of the documents to the sponsor. Study reports stored on computers must comply with local data protection laws. Patients will be

notified in writing that representatives of the sponsor, Ethics Committee/Institutional Review Board, or drug regulatory authorities may review their medical records to verify the information collected. All personal information involved in the review will be kept strictly confidential and will comply with local data protection laws. If the study results are published, the patient's personal identity will remain confidential. The investigator will retain a list to verify patient records.

### **III. Study Participant Recruitment**

#### **1. Inclusion Criteria**

- (1) stage III-IVa NPC (AJCC 8th edition) diagnosed via pathology in a tertiary hospital;
- (2) no previous radiotherapy, chemotherapy, surgery, immunization, or targeted therapy;
- (3) Karnofsky Performance Status score  $\geq 80$ ;
- (4) intact and normal oral mucosa before treatment;
- (5) age 18–75 years;
- (6) voluntary participation and provision of informed consent in person;
- (7) routine blood examination: white blood cell count  $\geq 4.0 \times 10^9/L$ , hemoglobin  $\geq 100g/L$ , neutrophil count  $\geq 1.5 \times 10^9/L$ , and platelet count  $\geq 100 \times 10^9/L$ ;
- (8) biochemical examination: total bilirubin  $\leq 1.5 \times$  the upper limit of the normal range (ULN), alanine aminotransferase and aspartate aminotransferase  $\leq 2 \times$  ULN, and estimated glomerular filtration rate  $\geq 60$  mL/min.

#### **2. Exclusion Criteria**

- (1) with other malignant tumors in the past or present and/or distant metastasis during treatment;
- (2) who have undergone surgery, chemoradiotherapy, and targeted immunotherapy;
- (3) with a history of asthma, rash, urticaria, and other allergic diseases;
- (4) with a history of autoimmune diseases, connective tissue diseases, and diabetes mellitus that significantly affect the healing of the oral mucosa;
- (5) with concomitant diseases, such as heart disease, kidney disease, and acute infectious diseases, which are judged by the investigator to seriously endanger the safety of patients or affect the completion of the study;
- (6) who are breastfeeding, pregnant, or planning to become pregnant during the study;
- (7) with known allergies to the therapeutic agents and penicillin used in the trial;
- (8) with mental or nervous system diseases or poor compliance will be excluded from the study.

### **3. Withdrawal and Termination Criteria**

#### **3.1 Withdrawal determined by the investigator**

Withdrawal determined by the investigator refers to situations where it is inappropriate for an already enrolled patient to continue the trial, and the investigator decides to withdraw the patient from the trial:

- ① The patient is unsuitable to continue receiving the trial treatment;
- ② The patient has poor compliance;
- ③ Occurrence of a serious adverse event or emergency unblinding in the trial;
- ④ Use of protocol-prohibited medications during the trial.

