# **Efficacy and Safety of Sapylin Versus Dexamethasone Atomized Inhalation for Concurrent Chemoradiotherapy-Induced Oral Mucositis in Patients With Nasopharyngeal Carcinoma: A Randomized, Parallel, Non-inferiority Clinical Trial**

## **I. Rationale**

### **1. Background**

Nasopharyngeal carcinoma (NPC), an epithelial malignancy originating from the nasopharyngeal mucosa, is one of the common head and neck malignancies. Globally, 70% of new cases occur in East and Southeast Asia. Nearly 80% of global patients are concentrated in China, leading to its nickname, "China Cancer". Within China, it is highly prevalent in the southern regions, especially the Guangdong, Guangxi areas and Hong Kong, hence the common name "Guangdong Cancer". Currently, radiotherapy is the primary treatment modality for NPC. Seventy percent of patients are diagnosed at an advanced stage. For Locally Advanced NPC (LA-NPC), induction chemotherapy combined with Concurrent Chemoradiotherapy (CCRT) is the standard treatment regimen. Since the adoption of induction chemotherapy combined with CCRT for LA-NPC patients, overall survival rates have improved. However, over 20% of LA-NPC patients still experience treatment failure and have a 5-year survival rate lower than 5 years. Furthermore, during radiotherapy, the radiation causes varying degrees of damage to the normal tissues adjacent to the tumor. Adverse reactions such as dry mouth and radiation-induced oral mucositis can reduce patient compliance. In severe cases, these can lead to clinical adverse outcomes such as reduced radiation dosage, treatment interruption, prolonged hospitalization, or even life-threatening situations, thereby negatively impacting the efficacy and quality of life associated with CCRT. The INT0099 trial showed that 37% of patients receiving CCRT terminated treatment prematurely due to excessive toxicity.

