## 6. Evaluation Indicators

- (1) Primary Evaluation Indicator: Incidence and severity of RIOM.
- (2) Secondary Evaluation Indicators: ①Duration of RIOM; ②Rate of completion of treatment measures; ③Adverse events classified according to CTCAE 5.0; ④Changes in BMI.

**Adverse Event (AE)** Any untoward medical occurrence in a subject during the clinical trial, which does not necessarily have a causal relationship with the treatment. An adverse event can be any unfavorable and unintended sign (including abnormal laboratory findings), symptom, or temporary illness associated with the use of the drug, whether or not related to the drug.

**Serious Adverse Event (SAE)** All serious adverse events occurring during the clinical trial must be recorded in the Serious Adverse Event (SAE) report. The occurrence of any of the following conditions should be considered a serious adverse event:

- ① Results in death;
- ② Is life-threatening;
- ③ Requires inpatient hospitalization or prolongation of existing hospitalization;
- ④ Results in persistent or significant disability/incapacity;
- ⑤ Results in a congenital anomaly or birth defect;
- ⑥ Other.

**Causality Assessment of Adverse Events** While recording in detail any abnormal symptoms, signs, laboratory tests, or other special examinations occurring during the clinical study, a causality assessment should be performed. According to the criteria for adverse reaction/event analysis, the causality assessment is classified as: 1-Definitely related; 2-Probably related; 3-Possibly related; 4-Probably unrelated; 5-Definitely unrelated.

- ① Is there a reasonable temporal relationship between the start of medication and the appearance of the suspected adverse reaction?
- ② Does the suspected adverse reaction fit the known adverse reaction profile of the drug? ③ Can the suspected adverse reaction be explained by the effects of concomitant medications, the patient's clinical condition, or other therapies?
- ④ Does the suspected adverse reaction disappear or alleviate after stopping or reducing the drug?
- ⑤ Does the same reaction reappear after re-exposure to the suspected drug?

Causality Determination Criteria: Determined sequentially according to the above indicators 1-5.

Causality Determination Table for Adverse Reactions					
Judgment Result	Assessment Indicators				
	①	②	③	④	⑤
Definitely Related	+	+	-	+	+

Probably Related	+	+	-	+	?
Possibly Related	+	+	+	±	?
Probably Unrelated	+	-	±	±	?
Definitely Unrelated	-	-	+	-	-

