#### ② Statistical Analysis Populations

**Full Analysis Set (FAS):** Refers to the ideal set of subjects that closely adheres to the intention-to-treat principle (including all randomized subjects who have received at least one treatment). This data set is formed by excluding randomized subjects using minimal and reasonable methods. For example, cases with no follow-up observation data after enrollment (no medication received) may be excluded. For the estimation of missing values for primary variables, such as case data where the entire treatment process was not observed, the last observation carried forward (LOCF, or "carry-forward") method will be used to impute missing trial data. The number of subjects evaluated for efficacy at the endpoint in each group will remain consistent with the number at the start of the trial.

**Per Protocol Set (PPS):** Includes all cases that comply with the trial treatment protocol, have good compliance (used the trial drug quantity between 80% and 120%), completed the required fields in the CRF, have measurable primary variables, have no missing baseline variables, and have no major violations of the trial protocol.

**Safety Analysis Set (SS):** Includes all enrolled cases that have used the study medication at

least once and have safety records after drug administration. This data set is used for safety analysis.

In this trial, baseline data will be analyzed using the FAS. Primary efficacy endpoints will be analyzed simultaneously on the FAS and PPS. Safety evaluation will be conducted using the SS.

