### **3.3 Handling of Dropouts**

When a patient drops out, the investigator must fill in the reason for dropout in the CRF. They should contact the patient whenever possible, complete all feasible assessment items, and fill in the end-of-treatment follow-up record form, recording the time of the last dose if possible. For dropouts due to an adverse event that is ultimately judged to be related to the study drug following follow-up, this must be recorded in the CRF and the sponsor notified. No replacement cases are needed for dropouts.

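### Investigator withdrawal ends trial participation without requiring RIOM grading to continue, and LOCF then carries Grade 0 forward for anyone withdrawn before onset

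*Protocol*

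**What the plan says.** Five places in the protocol bear on this.

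- **III.3.1, Withdrawal determined by the investigator.** For a patient who should not continue, "the investigator decides to withdraw the patient from the trial". The listed situations include "The patient has poor compliance", "Occurrence of a serious adverse event or emergency unblinding in the trial" and "Use of protocol-prohibited medications during the trial". The SAE item is not restricted to events related to study drug. Nothing separates stopping the nebulised drug from ending observation.
- **II.6, Evaluation Indicators.** An SAE includes an event that "Requires inpatient hospitalization or prolongation of existing hospitalization". The Background (I.1) lists "treatment interruption, prolonged hospitalization, or even life-threatening situations" among the consequences of severe radiation reactions, oral mucositis among them.
- **III.3.3, Handling of Dropouts.** The investigator is to contact the patient where possible, "complete all feasible assessment items, and fill in the end-of-treatment follow-up record form". Grading to the end of chemoradiotherapy is not required.
- **II.7(2)②, Statistical Analysis Populations.** Where the treatment course of a primary variable was not fully observed, the last-observation-carried-forward "method will be used to impute missing trial data" in the FAS. The number evaluated at the endpoint is kept equal to the number at the start.
- **III.3.4, Criteria for Case Exclusion.** Cases with missing major indicators are excluded, as are cases whose prohibited medication makes efficacy impossible to evaluate.

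The primary indicator is the incidence and severity of RIOM, graded on daily ward rounds (II.3.2(1)). Inclusion criterion 4 requires an intact, normal oral mucosa.

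**The concern.** Non-inferiority rests on a difference in RIOM incidence. RIOM develops over a six- to seven-week course, so a patient who leaves observation early has had less time to show it. Carrying the last grade forward treats that patient as if the rest of the course had been seen and nothing had happened. Every patient starts at Grade 0, so each withdrawal before onset is scored as a success.

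Withdrawal after onset acts differently. The incidence event is already recorded and LOCF keeps it. What can be lost is a later, worse grade, and the date of resolution that the duration endpoint needs (II.3.2(2)).

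The reasons for withdrawal (toxicity, compliance, other medication) can plausibly differ between an immune stimulant and a corticosteroid, and the protocol describes no blinding procedure. Pre-onset withdrawals could therefore differ by arm, and the difference compared with the margin would shift for a reason unrelated to RIOM.

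**Working it through.** **The plan's own figure.** Section II.3.3(2) needs 81 per group and allows 10% loss: 81 / 0.90 = 90 per group, 180 in total. This reproduces. The 81 itself cannot be checked, because no RIOM rates are stated.

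**Inputs for the illustration**

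- n = 90 per arm, because the FAS keeps endpoint numbers equal to starting numbers.
- Margin 8 percentage points. The protocol says 8% and does not name the scale, so this is an assumption.
- One-sided alpha 0.05 and 0.025. The protocol gives alpha 0.05 without saying whether the non-inferiority test is one- or two-sided.
- Control RIOM 68.75% (dexamethasone group of the retrospective series, section VIII) and 80% (the Background says over 80%).
- Sapylin truly worse by exactly 8 points: 76.75% and 88%.
- Share withdrawn before onset, w: assumed. The protocol gives only an overall 10% loss allowance, not split by arm.

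**Formulas**

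- Observed rate after LOCF: p × (1 − w)
- SE = √[p_S(1 − p_S)/90 + p_C(1 − p_C)/90], using the observed rates
- Probability of declaring non-inferiority: Φ((0.08 − observed difference)/SE − z), with z = 1.645 or 1.960

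**Worked case: control 68.75%, w = 10% Sapylin and 5% control**

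- Sapylin 0.7675 × 0.90 = 0.6908; control 0.6875 × 0.95 = 0.6531; difference 0.0376
- SE = 0.0699; (0.08 − 0.0376)/0.0699 = 0.606
- Φ(0.606 − 1.645) = 14.9%; Φ(0.606 − 1.960) = 8.8%

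**Results (true difference 8 points; the first figure in each pair is for control 68.75%, the second for 80%)**

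| Withdrawn before onset, Sapylin / control | Observed difference, points | False non-inferiority, 0.05 | False non-inferiority, 0.025 |
|---|---|---|---|
| 0 / 0 | 8.0; 8.0 | 5.0%; 5.0% | 2.5%; 2.5% |
| 10% / 10% | 7.2; 7.2 | 6.3%; 6.4% | 3.2%; 3.3% |
| 10% / 5% | 3.8; 3.2 | 14.9%; 19.2% | 8.8%; 11.8% |
| 5% / 10% | 11.0; 11.6 | 1.9%; 1.3% | 0.8%; 0.5% |

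Equal withdrawal shrinks a true difference by the factor (1 − w) and inflates the error slightly. Unequal withdrawal moves it much more, in whichever direction the imbalance runs. These figures apply to the FAS only and assume that every modelled withdrawal precedes onset.

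**The case against.** The case against a larger claim is strong, and most of it stands.

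- **Withdrawal is not automatic.** A reader might infer that every SAE removes a patient. Section III.3.1 covers situations where continuing is inappropriate and the investigator decides. The SAE item has no qualifier of its own, but the decision is discretionary.
- **The severe-RIOM route does not bias incidence.** It is tempting to chain severe mucositis, prolonged hospitalisation, SAE and withdrawal, and to conclude that the primary comparison is corrupted by its own outcome. That patient already has RIOM on record, and LOCF keeps it. The route affects worst grade and duration only. No text links withdrawal before onset to RIOM itself.
- **Direction is unknown.** A reader might infer that the rule hides inferiority of Sapylin. The protocol gives no withdrawal rates by arm. Its only toxicity data (section VIII, Table 2; 16 retrospective patients per group) show 25 grade III-IV entries for dexamethasone and 7 for Sapylin. If that carried over to early withdrawal, the bias would work against Sapylin.
- **Section III.3.3 asks for more than a form.** It asks for contact and all feasible assessments, so a worse grade can still be captured at the closing assessment. That grading then stops is an inference; ward rounds may continue in practice. The protocol does not require it, however, and II.7 provides for courses not fully observed.
- **Not every case is imputed.** Section III.3.4 excludes some of them, and the primary endpoint is also analysed on the PPS, which drops poor compliers and major violations. The PPS therefore holds fewer carried-forward Grade 0 values, but it does so by removing patients. Neither set recovers the missing grades.

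The point could also be left to a SAP. The analysis method could; the duty to keep collecting grades could not, because grades never collected cannot be restored later.

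**Conclusion.** The point holds in a limited form. The protocol does not separate stopping study drug from leaving the study, requires only a closing assessment after withdrawal, and prescribes LOCF for the primary variable. Followed as written, it scores patients withdrawn before onset as free of RIOM. After onset, incidence is safe, while worst grade and duration are exposed.

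The size depends on withdrawal shares that the documents do not give. Across the assumed scenarios, false non-inferiority in the FAS runs from 1.3% to 19.2% against a nominal 5%, or from 0.5% to 11.8% against 2.5%. The text does not support saying which way the trial would be biased. It supports saying that the incidence comparison is open to a shift of about 1 to 5 points (8.0 to 7.2 at the least, 8.0 to 3.2 at the most) on an 8-point margin, and that this can be avoided. Separately, II.7 imputes incomplete cases while III.3.4 excludes cases with missing major indicators, so the two must be reconciled.

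**What to change.** 1. In III.3.1 and III.3.3, distinguish a patient who stops study drug from one who leaves the study.
2. For every randomised patient who has not withdrawn consent to data collection, continue the existing ward RIOM grading to the end of radiotherapy, and keep the planned follow-up visits.
3. In II.7(2)②, analyse those observed grades in the FAS in place of LOCF values.
4. Reconcile III.3.4 with II.7(2)②, so that it is clear which incomplete cases stay in the FAS.

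The cost is a short protocol amendment and a few more follow-up records; the grading is already part of daily rounds. This takes no position on when study drug should be stopped.

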### **3.2 Subject initiated withdrawal**

In accordance with the informed consent form, the subject has the right to withdraw from the trial midway. A subject is also considered "withdrawn" if they do not explicitly request to withdraw but are lost to follow-up by no longer receiving medication and testing. The reason for withdrawal should be ascertained and recorded whenever possible. Examples include: feeling the treatment is ineffective; finding certain adverse reactions intolerable; having commitments preventing continuation of the clinical study; economic factors; or being lost to follow-up without stating a reason. Regardless of the reason, the case report form for the withdrawn patient should be retained.

### **3.3 Handling of Dropouts**

When a patient drops out, the investigator must fill in the reason for dropout in the CRF. They should contact the patient whenever possible, complete all feasible assessment items, and fill in the end-of-treatment follow-up record form, recording the time of the last dose if possible. For dropouts due to an adverse event that is ultimately judged to be related to the study drug following follow-up, this must be recorded in the CRF and the sponsor notified. No replacement cases are needed for dropouts.

### **3.4 Criteria for Case Exclusion**

- ① Case selection does not meet the inclusion criteria;
- ② The trial medication was never used;
- ③ No data exists after randomization or major indicators are missing, or the data is obviously incomplete;
- ④ Use of medications prohibited by the trial protocol, making efficacy evaluation impossible.

## **4. Duration of Participation (Time per session and total time)**

This study is expected to last 5 years, including an 48-month enrollment period. Each patient will be followed up for 12 months after stopping treatment.

- (1) Planned date for enrollment of the first patient: July 30, 2022.
- (2) Planned date for enrollment of the last patient: July 1, 2026.
- (3) Planned date for the last patient's exit or trial conclusion: July 1, 2027.
- (4) Estimated report date: July 20, 2027.
- (5) Follow-up duration: 12 months; Primary endpoint: Incidence and severity of RIOM; Secondary endpoints: ①Duration of RIOM; ②Rate of completion of treatment measures; ③Adverse events classified according to CTCAE 5.0; ④Changes in BMI

Follow-up frequency: The follow-up period is 1 year; The first follow-up is 1 month after concurrent chemoradiotherapy; thereafter, follow-up visits are every 3 months. RIOM incidence rate, severe RIOM incidence rate, ORR, and PFS.

## **5. Recruitment Process (Including recruitment procedure and start time, recruitment materials, expected number of recruits)**

- (1) Patient selection: Meeting the diagnostic criteria for NPC; patients who have not yet received concurrent chemoradiotherapy; meeting the inclusion and exclusion criteria; patients voluntarily joining this clinical trial and signing the informed consent form.
- (2) Expected number of recruits: The Delphi method is used to determine the non-inferiority margin of the observation endpoint. After consulting senior oncology practitioners, we defined an

8% reduction in the incidence of RIOM as a clinically acceptable non-margin of error. Under the conditions of test level  $\alpha=0.05$  and test efficacy  $1-\beta=0.9$ , the proportion of cases in the two groups is 1:1. Using the module of non-destructiveness Tests for Two Proportions in PASS 15.0 statistical analysis software, we determined that a sample size of 81 was required per group. Considering a 10% loss to follow-up rate, we estimated that 90 cases would be required in each group, for a total of 180 cases.

(3) Planned date for enrollment of the first patient: July 30, 2022; Planned date for enrollment of the last patient: July 1, 2026; Planned date for the last patient's exit or trial conclusion: July 1, 2027.

